5.6 Rescue Medications & Supportive Care

5.6.1 Supportive Care Guidelines

Subjects should receive appropriate supportive care measures as deemed necessary by the treating investigator. Suggested supportive care measures for the management of AEs with potential immunologic etiology associated with pembrolizumab are outlined along with the dose modification guidelines in Section 5.2.1.2, [Table 10](#). Additional toxicity management guidelines are provided below in [Table 16](#) to [Table 35](#). Where appropriate, these guidelines include the use of oral or IV treatment with corticosteroids, as well as additional anti-inflammatory agents if symptoms do not improve with administration of corticosteroids. Note that several courses of steroid tapering may be necessary as symptoms may worsen when the steroid dose is decreased. For each disorder, attempts should be made to rule out other causes such as metastatic disease or bacterial or viral infection, which might require additional supportive care. The treatment guidelines are intended to be applied when the Investigator determines the events to be related to study treatment.

Note: If after the evaluation of the event, it is determined not to be related to pembrolizumab, the Investigator does not need to follow the treatment guidance. Refer to [Table 10](#) in Section 5.2.1.2 for guidelines regarding dose modification and supportive care.

It may be necessary to perform conditional procedures such as bronchoscopy, endoscopy, or skin photography as part of evaluation of the event.

Adverse Event Management Guidelines, including dose modification algorithms, are provided in this section for subjects treated with:

- Trametinib+dabrafenib
- Pembrolizumab (or saline IV)+trametinib and/or dabrafenib
- Pembrolizumab

Note: Dose modification guidelines for a given toxicity (e.g., hepatotoxicity) may not be identical for each treatment; therefore it is important to refer to the algorithm described for the combination treatment or specific single-agent. An overview of the available dose modification guidelines is presented in [Table 16](#) along with the location of the toxicity- and treatment-specific guidance.

All AEs are to be graded according to NCI-CTCAE v4 (<http://ctep.cancer.gov>). All dose modifications and the reason for the dose modification must be documented in the eCRF.

Investigators should refer to the appropriate IB for trametinib, dabrafenib and pembrolizumab for additional information regarding the background of each drug and the management of other AEs or potential safety-related issues.

Events of Clinical Interest (ECIs) are selected non-serious and serious adverse experiences that must be reported to Merck **within 24 hours** regardless of attribution to trial treatment.

5.6.1.1 Pembrolizumab+Trametinib and/or Dabrafenib, or, Trametinib+Dabrafenib Combination Safety Management Guidelines

Dose modifications and stopping criteria for the management of toxicities are presented in this section for subjects treated with the combination of dabrafenib and/or trametinib +/- pembrolizumab. Toxicities common to dabrafenib, trametinib, and pembrolizumab include, but are not limited to, ocular toxicities, skin-related toxicities, diarrhea, pneumonitis, and pyrexia. Therefore, it is possible that these and/or other toxicities may be exacerbated when dabrafenib, trametinib, and pembrolizumab are combined. For this reason, it is important to note that the management guidelines for the combination of dabrafenib + trametinib + pembrolizumab may differ for a given AE from the management guidelines for single-agent dabrafenib, single-agent trametinib, combination of dabrafenib+trametinib, or single-agent pembrolizumab.

5.6.1.1.1 Dose Level Reduction of Trametinib and/or Dabrafenib for Subjects beyond the DLT Period

The dose level reductions for subjects beyond the DLT evaluation period for dabrafenib and trametinib for this study are provided in [Table 5](#) and [Table 16](#).

Table 16 Dose Level Reduction Guidelines

Dose Level	Dabrafenib Dose/Schedule	Trametinib Dose/Schedule
Starting Dose	150 mg BID	2 mg once daily
-1 (1 st Dose reduction)	100 mg BID	1.5 mg once daily
-2 (2 nd Dose reduction)	75 mg BID	1.0 mg once daily
Abbreviation: BID = twice daily		

If an AE resolves to grade 1 or baseline at the reduced dose level, and no additional toxicities are seen after 4 weeks of study treatment at the reduced dose, the dose may be increased to the previous dose level after discussion with the Sponsor. Please refer to Section 5.2.1.2.1 and Section 5.6.1.1 for additional information on dose modification and associated supportive care guidelines for pembrolizumab, trametinib, and/or dabrafenib.

5.6.1.1.2 Interruption or Discontinuation of Trametinib, Dabrafenib and/or Pembrolizumab

If a subject's study treatment has been interrupted for more than 21 days for dabrafenib, trametinib, and/or 2 doses of pembrolizumab have been withheld, the investigator must contact the Sponsor to review the subject's condition in order to resume the treatment.

Subjects being treated on combination therapy who require discontinuation of one or more medications for toxicity may continue the remaining treatment(s). The reason for

discontinuation must be recorded. For subsequent management of toxicities on the remaining treatment(s), please refer to the relevant IB for the medication.

5.6.1.1.3 Immune-related Adverse Events

Adverse events of special interest of a potential immunologic etiology may be defined as an adverse event associated with drug exposure and consistent with an immune phenomenon. irAEs may be predicted based on the nature of the pembrolizumab compound, its mechanism of action, and reported experience with immunotherapies that have a similar mechanism of action. Special attention should be paid to AEs that may be suggestive of potential irAEs. An irAE can occur shortly after the first dose or several months after the last dose of treatment.

General principles of irAE identification and evaluation:

Before each dose investigators are to review a subject's AEs, concomitant medications and clinical evaluation results e.g., vital signs, laboratory results, physical exam findings, etc., as outlined in Section 7.1 to monitor for new or worsening irAEs and ensure continued dosing is appropriate.

Early recognition of irAEs and initiation of treatment are critical to reduce the risk of complications, since the majority of irAEs are reversible with the use of steroids and other immune suppressants [93-95]. If an irAE is suspected, the subject should return to the study site as soon as possible instead of waiting for their next scheduled visit. Subjects who experience a new or worsening irAE should be contacted and/or evaluated at the study site more frequently.

If an irAE is suspected, a thorough evaluation should be conducted in an effort to possibly rule out neoplastic, infectious, metabolic, toxin or other etiologic causes before diagnosing an irAE. Serological, immunological, and histological (biopsy) data should be considered to support the diagnosis of an immune-related toxicity. Higher grade and persistent lower grade irAEs typically necessitate interrupting or permanently discontinuing treatment and administration of systemic steroids or other immunosuppressive agents (such as TNF blockers) when systemic steroids are not effective.

Identification and treatment of irAEs: Based on literature review and consideration of mechanism of action of pembrolizumab, guidelines have been developed regarding how to identify, evaluate and manage irAEs that may occur in subjects receiving pembrolizumab (see Section 5.2.1.2.1). It is possible that irAEs other than those listed in this document may be observed in subjects receiving pembrolizumab, therefore all AEs of unknown etiology associated with drug exposure should be evaluated to determine if it is possibly immune-related. This section is meant to be a general guidance; therefore, recommendations in the current document might not be all inclusive. As such investigators are encouraged to contact the Sponsor as needed to discuss cases that warrant separate discussion outside of the scope of current guidelines. Permanent discontinuation of pembrolizumab, trametinib, and/or

dabrafenib due to an irAE may be the subject of discussion between the Sponsor and treating investigator.

Subjects should be followed to resolution. The Adverse Experience eCRF should be updated with information regarding duration and clinical course of the event. Information obtained from the consulting specialist, including diagnosis, should be recorded in the appropriate AE fields. Free-text fields should be used to record narrative information:

- Clinical course of the event
- Course of treatment
- Evidence supporting recovery
- Follow-up to the clinical course

Any treatments administered for the event should also be entered in the Concomitant Medication eCRF.

5.6.1.1.4 General Guidelines for Clinically Significant Toxicities

General guidelines regarding management and dose reduction for adverse events that are considered by the investigator to be related to study treatment and which do not have specific guidelines are provided in [Table 17](#).

Table 17 Dose Modification Guidelines for Events Considered Related to Study Treatment

CTCAE Grade	Action and Dose Modification
Grade 1 or Grade 2 (tolerable)	
 Continue study treatment at current dose level Monitor closely Provide supportive care according to institutional standards
Grade 2 (Intolerable)	
 Interrupt study treatment if clinically indicated Monitor closely Provide supportive care according to institutional standards 
 If treatment was interrupted, when toxicity resolves to grade 1 or baseline, restart study treatment: dose-reduced for 1st or 2nd occurrence (dabrafenib and/or trametinib only) if > 2 dose-reductions are required, permanently discontinue study treatment
Grade 3	
 Interrupt study treatment Monitor closely Provide supportive care according to institutional standards When toxicity resolves to grade 1 or baseline, restart study treatment reduced by one dose level or discontinue at investigator's discretion after discussion with sponsor If the grade 3 toxicity recurs, interrupt study treatment When toxicity resolves to grade 1 or baseline, restart study treatment reduced by another dose level or discontinue at investigator's discretion after discussion with sponsor Discontinue study treatment at next occurrence
Grade 4	
 Interrupt study treatment Permanently discontinue pembrolizumab Monitor closely Provide supportive care according to institutional standards May restart dabrafenib and/or trametinib reduced by one dose level once toxicity resolves to grade 1 or baseline, or discontinue at investigator's discretion If the grade 4 toxicity recurs, either permanently discontinue all study treatment or, if the subject is clinically benefiting, discuss continuation of study treatment with the Sponsor.
Any Grade^a	
 Any signs of symptoms of Severe Cutaneous Adverse Reactions (SCARs), permanently discontinue dabrafenib and trametinib immediately

a. Cases of SCARs, including Stevens-Johnson syndrome, and drug reaction with eosinophilia and systemic symptoms, which can be life-threatening or fatal, have been reported during treatment with dabrafenib in combination with trametinib. Before initiating treatment, patients should be advised of the signs and symptoms and monitored closely for skin reactions. If signs and symptoms suggestive of SCARs appear, dabrafenib and trametinib should be permanently discontinued.

Note: With the exception of cases of SCARs, when an individual subject's adverse reactions are effectively managed, dose re-escalation following the same dosing steps as de-escalation may be considered.

5.6.1.1.5 Diarrhea

Subjects should be carefully monitored for signs and symptoms of enterocolitis (such as diarrhea, abdominal pain, blood or mucus in stool, with or without fever) and of bowel perforation (such as peritoneal signs and ileus).

All subjects who experience diarrhea/colitis should be advised to drink liberal quantities of clear fluids. If sufficient oral fluid intake is not feasible, fluid and electrolytes should be substituted via IV infusion. For Grade 2 or higher diarrhea, consider GI consultation and endoscopy to confirm or rule out colitis.

All attempts should be made to rule out other causes such as metastatic disease, bacterial or parasitic infection, viral gastroenteritis, or the first manifestation of an inflammatory bowel disease by examination for stool leukocytes, stool cultures, and a Clostridium difficile titer.

Episodes of diarrhea have occurred in subjects receiving dabrafenib, trametinib, or both therapies in combination, as well as in subjects receiving pembrolizumab. Other, frequent causes for diarrhea including concomitant medications (e.g., stool softeners, laxatives, antacids, etc.), infections by C. difficile or other pathogens, partial bowel obstruction, etc., should be clinically excluded.

Guidelines regarding management and dose reduction for diarrhea considered to be related to study treatment by the investigator are provided in [Table 10](#) and [Table 18](#).

Table 18 Management and Dose Modification Guidelines for Diarrhea

CTCAE Grade	Adverse Event Management	Action and Dose Modification
Uncomplicated Diarrhea ^a Grade 1 or 2	
 Diet: stop all lactose containing products; eat small meals, ADA colitis diet recommended Hydration: 8-10 large glasses of clear liquids per day (e.g., Gatorade or broth) Consider GI consultation and endoscopy to evaluate for colitis for Grade 2 diarrhea persisting > 1 week If symptoms worsen or persist > 3 days, treat as Grade 3 Loperamide^c: initially 4 mg, followed by 2 mg every four hours or after every unformed stool; maximum 16 mg/day. Continue until diarrhea free for 12 hours. Diarrhea > 24h: loperamide 2 mg every two hours; maximum 16 mg/day. Consider adding oral antibiotics. Diarrhea > 48h: loperamide 2 mg every two hours; maximum 16 mg/day. Add budesonide (9mg/day) or other second-line therapies (octreotide, oral diphenoxylate hydrochloride, atropine sulfate four times daily, or tincture of opium) and oral antibiotics Grade 2 diarrhea with diffuse ulceration and bleeding seen on endoscopy or lasting >1 week may require oral steroids with prolonged taper and represent an increased risk for the development of bowel perforation. When symptoms improve to Grade 1 or less, steroid taper should be started and continued over no less than 4 weeks. 	
 Continue study treatment, unless: If diarrhea is grade 2 for > 48h: interrupt study treatment until diarrhea resolves to grade ≤ 1. Restart study treatment at the same dose level.

CTCAE Grade	Adverse Event Management	Action and Dose Modification

Uncomplicated Diarrhea^a Grade 3 or 4
 
OR
 
Any Complicated Diarrhea^b
	
 Clinical evaluation mandatory; rule out bowel perforation Consider consultation with Gastroenterologist and confirmation biopsy with endoscopy Loperamide^c: initially 4 mg, followed by 2 mg every four hours or after every unformed stool; maximum 16 mg/day. Continue until diarrhea free for 12 hours Hydration: intravenous fluids if clinically indicated Antibiotics (oral or intravenous) if clinically indicated Intervention should be continued until the subject is diarrhea free for \geq 24 hours In addition to symptomatic treatment and hydration, immediate treatment with intravenous steroids (methylprednisolone 125 mg) followed by high dose oral steroids (prednisone 1 to 2 mg/kg once per day or dexamethasone 4 mg every 4 hours) is recommended. When symptoms improve to \leqGrade 1, steroid taper should be started and continued over no less than 4 weeks. Taper over 6 to 8 weeks in subjects with diffuse and severe ulceration and/or bleeding. If IV steroids followed by high dose oral steroids do not reduce initial symptoms within 48 to 72 hours, consider alternative treatment. Discontinue alternative treatment upon symptom relief and initiate a prolonged steroid taper over 45 to 60 days. If symptoms worsen during steroid reduction, initiate a re-tapering of steroids starting at a higher dose of 80 or 100 mg followed by a more prolonged taper and administer infliximab. If symptoms persist despite the above treatment a surgical consult should be obtained. Intervention may require hospitalization for subjects at risk of life-threatening complications 	
Grade 3
 
 Interrupt all study treatment until diarrhea resolves to grade \leq1 pembrolizumab may be restarted after diarrhea resolves to grade \leq1 and steroid taper (if initiated) is completed Restart dabrafenib and/or trametinib reduced by one dose level^d 
 If dabrafenib and/or trametinib was already dose reduced twice, permanently discontinue dabrafenib and/or trametinib. 
Grade 4
 
 Permanently discontinue pembrolizumab Follow Grade 3 rules for dabrafenib and/or trametinib.

Abbreviation: CTCAE = Common Terminology Criteria for Adverse Events
 
a. Uncomplicated diarrhea defined by the absence of symptoms such as, cramping, nausea/vomiting \geqgrade 2, decreased performance status, pyrexia, sepsis, neutropenia grade \geq3, frank bleeding, and/or dehydration requiring intravenous fluid substitution
 
b. Complicated diarrhea defined by the presence of symptoms such as, cramping, nausea/vomiting \geqgrade 2, decreased performance status, pyrexia, sepsis, neutropenia grade \geq3, frank bleeding, and/or dehydration requiring intravenous fluid substitution
 
c. Loperamide should be made available prior to start of study treatment so loperamide administration can begin at the first signs of diarrhea
 
d. Escalation of study treatment to previous dose level is allowed after consultation with the Sponsor and in the absence of another episode of complicated or severe diarrhea in the 4 weeks subsequent to dose reduction.
		

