Pneumonitis (see also Table 22)	Grade 2	Withhold	
 • Administer corticosteroids (initial dose of 1-2 mg/kg prednisone or equivalent) followed by taper 	
 • Monitor participants for signs and symptoms of pneumonitis • Evaluate participants with suspected pneumonitis with radiographic imaging and initiate corticosteroid treatment • Add prophylactic antibiotics for opportunistic infections
	Grade 3 or 4, or recurrent Grade 2	Permanently discontinue		
Diarrhea / Colitis (see also Table 18)	Grade 2 or 3	Withhold	
 • Administer corticosteroids (initial dose of 1-2 mg/kg prednisone or equivalent) followed by taper 	
 • Monitor participants for signs and symptoms of enterocolitis (ie, diarrhea, abdominal pain, blood or mucus in stool with or without fever) and of bowel perforation (ie, peritoneal signs and ileus). • Participants with \geq Grade 2 diarrhea suspecting colitis should consider GI consultation and performing endoscopy to rule out colitis. • Participants with diarrhea/colitis should be advised to drink liberal quantities of clear fluids. If sufficient oral fluid intake is not feasible, fluid and electrolytes should be substituted via IV infusion.
	Grade 4	Permanently discontinue		

Immune-related AEs	Toxicity grade or conditions (CTCAEv4.0)	Action taken to pembrolizumab	irAE management with corticosteroid and/or other therapies	Monitor and follow-up
AST / ALT elevation or Increased bilirubin See also Section 5.6.1.1.15	Grade 2	Withhold See also Table 30	
 Administer corticosteroids (initial dose of 0.5-1 mg/kg prednisone or equivalent) followed by taper 	
 Monitor with liver function tests (consider weekly or more frequently until liver enzyme value returned to baseline or is stable)
	Grade 3 or 4	Permanently discontinue Note: For Grade 3 events see Table 30 for detailed management and dose modification guidelines based on specific hepatic laboratory abnormalities	
 Administer corticosteroids (initial dose of 1-2 mg/kg prednisone or equivalent) followed by taper 	

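### Table 18 gives two restart instructions for uncomplicated Grade 2 diarrhea lasting over 3 days, and Tables 10 and 18 disagree on holding pembrolizumab at Grade 2

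*Combined protocol and SAP*

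**What the plan says.** Section 5.6.1.1.5 introduces its tables with "Guidelines regarding management and dose reduction for diarrhea considered to be related to study treatment by the investigator are provided in" Tables 10 and 18, and gives no order of precedence.

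**Table 18, uncomplicated Grade 1 or 2.**
- The action column begins "Continue study treatment, unless" and lists one exception: Grade 2 lasting more than 48 hours is interrupted until Grade 1 or lower. It then says "Restart study treatment at the same dose level", with no upper limit on duration.
- The management column says "If symptoms worsen or persist > 3 days, treat as Grade 3". It also adds budesonide or another second-line therapy once diarrhea passes 48 hours. It says "Consider GI consultation and endoscopy to evaluate for colitis for Grade 2 diarrhea persisting > 1 week", and it allows for oral steroids when Grade 2 shows diffuse ulceration and bleeding or lasts over a week.

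**Table 18, Grade 3.** The action is "Interrupt all study treatment until diarrhea resolves to grade" 1 or lower, then "Restart dabrafenib and/or trametinib reduced by one dose level". A kinase inhibitor already reduced twice is stopped for good. The management column recommends immediate intravenous methylprednisolone followed by high-dose oral steroids.

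**Table 10 (Section 5.2.1.2.1).** The diarrhea/colitis row, which cross-refers to Table 18, withholds pembrolizumab for Grade 2 or 3 and gives corticosteroids starting at 1-2 mg/kg prednisone or equivalent. It sets no duration condition.

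**The concern.** A site that reads across the Grade 1-2 row of Table 18 meets two answers for one patient once diarrhea passes 3 days. A site that opens Table 10 as well meets a second answer on pembrolizumab from the first day of Grade 2. The choice affects whether treatment is interrupted, whether systemic steroids are given during immunotherapy, and the dose at which dabrafenib and/or trametinib resume. Section 5.6.1.1 names diarrhea among the toxicities common to all three drugs, so the event is an expected one. Subjects still on treatment after the Part 3 unblinding remain under these guidelines (Section 8.2.1).

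**Working it through.** No power or error-rate figure is involved. The check sets the instructions side by side; the only arithmetic is the size of one dose step in Table 16 (Section 5.6.1.1.1).

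**Case A: uncomplicated Grade 2, day 4, starting doses.**
- Action column of the Grade 1-2 row: interrupt, then resume dabrafenib 150 mg BID and trametinib 2 mg once daily.
- Three-day line in the management column, followed into the Grade 3 action column: interrupt, then resume one level lower, at dabrafenib 100 mg BID and/or trametinib 1.5 mg once daily.
- Size of the step: dabrafenib (150 − 100)/150 = 33% lower, or 300 to 200 mg per day; trametinib (2 − 1.5)/2 = 25% lower.
- If two reductions have already been made, the two readings are restart unchanged or discontinue permanently.
- Both readings interrupt treatment by day 4. They part on restart level and steroids.

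**Case B: uncomplicated Grade 1, day 4.**
- Action column: continue. The only listed exception is for Grade 2.
- Three-day line, followed into the Grade 3 action column: interrupt all treatment and restart the kinase inhibitor(s) reduced.

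**Case C: steroids for uncomplicated Grade 1 or 2, day 4.**
- Three-day line, followed into the Grade 3 management column: intravenous, then high-dose oral steroids.
- Remaining lines of the Grade 1-2 cell: budesonide or another second-line therapy from 48 hours, with oral steroids a possibility for Grade 2 only with ulceration and bleeding or after more than a week.
- A cell that moves the event to Grade 3 after 3 days leaves no evident role for its own one-week provisions for Grade 2.

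**Case D: uncomplicated Grade 2, first 48 hours, pembrolizumab.**
- Table 10: withhold and give corticosteroids.
- Table 18: continue study treatment, which includes pembrolizumab.

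Cases A to C arise inside Table 18 alone. Case D is the only conflict between the tables. Table 10's action column covers pembrolizumab only, so it cannot produce a different kinase-inhibitor dose.

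**The case against.** The best defense of Table 18 is its layout. The three-day line sits in the management column among diet, hydration and loperamide, while dose action has its own column. Read as supportive care only, it leaves the restart level untouched, and Cases A and B dissolve as to dose and interruption. The text does not state that limit, however, and Case C survives it: the Grade 3 management cell is exactly where the intravenous and high-dose oral steroids stand.

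For Case D, Table 10 is headed for immune-related events and asks for the cause to be evaluated. Section 5.6.1 warns that algorithms may differ by treatment and releases the investigator from the pembrolizumab guidance when an event is judged unrelated to pembrolizumab. Section 5.6.1.1 adds that guidance for the combination may differ from single-agent guidance. This softens the conflict. It does not remove it, because Section 5.6.1.1.5 cites both tables for the same event, and Section 7.2.4 says causality should in general be assigned to the whole regimen. Nor can these notes settle a conflict inside one table.

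Several stronger readings are tempting, and the documents do not support them:
- **Bias in Part 3.** The final analysis is done (Section 5.2.5), and Section 8.2.1 provides for unblinding after its database lock, with controls continuing without placebo. The same text applied to both arms of a blinded 1:1 comparison, and nothing shows a differential effect.
- **Altered DLT counts.** No criterion in Section 5.2.4.3 turns on restart level. The interruption criterion needs more than 21 consecutive days together with lack of control within 2 weeks, and the Table 16 steps are for subjects beyond the DLT period. A route through the 66% evaluability rule is conceivable, but no figure supports it.
- **Stepped time limits as an error in themselves.** Successive triggers at 48 hours, 3 days and 1 week can coexist. The fault is that the actions attached to them conflict.

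**Conclusion.** The point holds as a conflict of instructions in the current text. Within Table 18, uncomplicated Grade 2 beyond 3 days can lead to restart doses up to one level apart: 33% for dabrafenib and/or 25% for trametinib from the starting doses. After two earlier reductions the difference is between an unchanged dose and permanent discontinuation. Grade 1 beyond 3 days and the steroid lines conflict as well. Between the tables, the difference is whether pembrolizumab is held, with corticosteroids, during the first 48 hours of Grade 2.

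The dose figures are upper limits. They assume that the three-day line carries the Grade 3 dose rules with it, and the text leaves open whether one or both drugs are reduced. Table 18 footnote d allows later re-escalation after Sponsor consultation and 4 weeks without another complicated or severe episode. Parts 4 and 5 use no dabrafenib, so only the trametinib figure can apply there. Case D assumes an event judged related to pembrolizumab. The documents give no event frequency and no site-level data, so it cannot be said how often sites diverged; a reader might infer that they did, but the text shows only that they could. What is at stake is subject safety and uniform handling for those still on treatment.

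**What to change.** The sponsor should reconcile the passages by amendment:
- State whether the three-day line in Table 18 covers supportive care only or also the Grade 3 interruption and dose-level rules.
- Make the steroid lines in the Grade 1-2 row consistent with that answer.
- State which of Tables 10 and 18 governs pembrolizumab for Grade 2 diarrhea when both apply.

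The clinical team decides which rules stand; this review proposes no duration trigger, dose or hold rule. The cost is amendment wording and a site memo, with no new data or subjects.
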